1.2 Risk/Benefit Assessment

To date, 11 Phase 1 studies in healthy volunteers and 3 Phase 2 studies in subjects suffering from depression have been performed with litoxetine. One in vitro study in human blood has been performed to evaluate plasma protein binding in humans.

Litoxetine has been evaluated in 154 healthy subjects and 445 patients with depression either as a capsule or a tablet containing litoxetine drug substance with excipients. Clinical pharmacology data has shown that doses up to 50 mg BID were acceptable, the open-label Phase 2 study in depression explored doses up to 100 mg daily, and subsequent double-blind, placebo-controlled studies explored doses up to 60 mg daily for a duration of 6 weeks. While study effects were observed in subjects with depression, the efficacy of litoxetine compared to placebo was negligible. In these studies, litoxetine safety information did not show any negative cardiovascular effects. The most common AEs were headache, nausea, and dyspepsia. The safety profile of litoxetine is acceptable and in line with the known and well established safety profile of 5-HT reuptake inhibitors. No AEs in the clinical studies have been reported which would preclude development of litoxetine in the new indication of Urinary Incontinence and Adverse Events will continue to be monitored throughout the study, including AEs of special interest (i.e., urinary retention, psychiatric adverse events and withdrawal effects).

Non-clinical studies have demonstrated effects of litoxetine on urethral sphincter and bladder capacity, which are key features for micturition and continence. The "dual action"-inhibitory effect on detrusor muscle activity and excitatory effect on urethral sphincter- provides a scientific rationale to evaluate whether litoxetine treatment may be a treatment option for subjects with UI. One phase 2 study is currently ongoing with litoxetine in women suffering from MUI, and, while early in its conduct, the adverse events reported to date confirm the data previously reported.

The safety and tolerability of litoxetine was mainly determined on data from 445 subjects included in depression studies, receiving daily doses up to 100 mg daily, up to 6 weeks duration, to support the current use of litoxetine at doses 20, 40, and 60 mg daily (10, 20 and 30 BID) for the currently proposed 8-week treatment period, while the non- clinical pharmacology supports the scientific rationale to evaluate litoxetine in the indication of UI. The safety data from the comprehensive nonclinical study program support the proposed Phase I/IIa study. Further details can be found in the Investigator's Brochure (Edition 3, Feb 2018).

Serotonin plays an important role in centrally modulating the reflexes of continence/micturition; 5-HT potentiates the guarding reflex which allows continence by increasing urethral pressure and inhibits the micturition reflex responsible for voiding. Animal studies have shown that increased levels of 5-HT and norepinephrine (NE), in the sacral spinal cord, lead to increased urethral tone via enhanced pudendal nerve stimulation to the urethral striated sphincter muscle during the storage phase of the micturition

cycle. Studies with duloxetine support a similar mechanism in women, believed to result in stronger urethral closure during urine storage with physical stress.

Animal studies have confirmed that litoxetine increases the urethral sphincter pressure, and also demonstrated that litoxetine improves bladder capacity through a relaxation effect of the detrusor. Taken together these effects suggest that litoxetine could have therapeutic benefit in Urinary Incontinence, a condition for which there remain an unmet medical need.

The 5-HT selectivity of litoxetine, and the weaker affinity for NE and epinephrine (E) as well as for dopamine (DA) transporters has the potential to provide a good cardiovascular safety profile, and reduce the risk of nausea which is the most frequent side effect following treatment with 5 HT reuptake inhibitors.

Further details can be found in the Investigator's Brochure (Edition 3, Feb 2018), which contains comprehensive information on the investigational product.

Taken together the Risk/Benefit for the use of litoxetine in the proposed study phase 1/2a is considered acceptable.

1.3 Rationale

Urinary incontinence is a condition which can have a significant negative impact on the psychological well-being, social functioning and overall quality of life of those affected. There remains an unmet medical need to identify treatment options for patients suffering from UI. The “dual action”-inhibitory effect on detrusor muscle activity and excitatory effect on urethral sphincter- provides a scientific rationale to evaluate whether litoxetine treatment may be a treatment option for UI.

1.4 Statistical Analysis Plan Summary (SAP)

This Statistical Analysis Plan (SAP) describes the statistical analysis for the IXA-CSP-002 study. The SAP provides full details of the analyses, the data displays and the algorithms to be used for data derivations. The analysis will be done using the statistical software SAS version 9.4 or higher.

1.5 Clarifications from Protocol

- a. Efficacy analysis of nocturia events has been added, although not specifically laid out in the protocol, since this data is captured in the bladder diary and nocturia episodes are of relevance for the wellbeing of the patient.
- b. The protocol includes an mITT population, which has been omitted from analyses since it was determined that the ITT and PP population will adequately describe the data.
- c. The methodology described in the protocol for the efficacy analyses is a mixed model with repeated measures (MMRM). In light of the fact that the efficacy measurements were recorded at visit 2 and visit 6 only, there are no repeated measures. Therefore, the MMRM model described in the protocol cannot be applied to these analyses. The efficacy analyses will be conducted as an analysis of covariance (ANCOVA).
- d. The description of the efficacy endpoints in the protocol is clarified to be:
 - a. Percentage change in number of incontinence episodes that a subject had in a week
This analysis is consistent with the analysis conducted for the phase 2 study IXA CSP 001

1.6 Study Summary

This is a Phase 1/2a, double-blind, randomised, placebo-controlled, parallel-group study in subjects, male and female, 18 to 70 years old diagnosed with UI.

The study will include a 2-week, single-blind (subject blind) Screening Placebo Run-In Period and an 8-week double-blind Treatment Period. The treatment period is a dose titration posology starting with 10 mg BID for 1 week, escalated to 20 mg BID for 1 week, and subsequently escalated to 30 mg BID for 6 weeks for a total treatment duration of 8 weeks. The Treatment Period will be followed by a 1 week Dose-tapering Period and subjects will return to the clinic for a safety Follow up Visit 4 weeks after treatment is completed. This provides a total study duration of 15 weeks.

Safety assessments will be conducted throughout the trial and will include physical examinations, vital signs, evaluation of psychiatric status (suicidality, depression symptoms, anxiety and sleep related symptoms), clinical laboratory evaluations, 12-lead electrocardiograms (ECGs), and adverse events (AEs).

Efficacy will be assessed by number of urinary incontinence episodes and the number of incontinence pads used at the end of the Placebo Run In period and after 8 weeks of double blind study treatment.

Approximately 95 subjects are expected to be enrolled into a 2 week, single-blind (subject blind), Screening Placebo Run-In Period. It is expected that 20% of subjects will not qualify for randomization after Screening Placebo Run-In.

The study is expected to randomize approximately 78 subjects into the double-blind treatment where subjects will be allocated to litoxetine (dose titration 10 mg, 20 mg, 30 mg) or matched placebo BID in a 2:1 ratio. A post randomisation dropout rate of 30% has been estimated, resulting in 60 evaluable subjects. This sample size is expected to provide confidence intervals for the most conservative rate of safety events (50%) that are +/- 14% for the widest observed intervals in the treatment arm.

The present study, for which safety is the primary endpoint, will include patients diagnosed with UI and is designed as a phase 1/2a study. The inclusion of a placebo arm is based on recent European Medicines Agency (EMA) guidelines for the development of medications for UI (European Medicines Agency, UI Guideline 2013). The dose titration posology serves to explore safety and tolerability following a sequential increase in dose, rather than as a fixed dose regimen. The selection of safety parameters for determination of subject eligibility and for safety analysis reflect the FDA's recommendation for evaluation of SSRIs, including attention to psychiatric adverse events and events indicative of abuse potential. Inclusion of subjects in the age range 18-70 is reflective of the expectation that UI may affect all age groups, with increasing prevalence with age (FDA Guidance General Consideration for the Clinical Evaluation of Drugs). The choice of efficacy endpoint (percentage change from end of the Placebo Run-in Period to Week 8 in the number of incontinence episodes/24 hours) is a clinical measure to explore whether litoxetine has a clinically relevant treatment effect on patients' reported symptomatology and patient reported outcome measures in a clinical practice setting. The 2-week Screening Placebo Run-In Period serves to control for the placebo effect which is anticipated to be relatively large.

[1.7 Version History](#)

SAP version history:

SAP v1.3 – Final (2nd April 2019).

SAP v1.2 – Draft 4 (25th March 2019).

SAP v1.1 – Draft 3 (21th February 2019).

SAP v1.0 – Draft 2 (18th February 2019).

SAP v0.1 – Draft version (8 November 2018).

Study protocol version history:

Version 1 Final Sep 14, 2017

Version 2 Amendment 1, June 28, 2018

Version 3 Amendment 2, October 10, 2018

2. Study Objectives

2.1 Primary Objective

The primary objective of this study is to evaluate the safety and tolerability of litoxetine (dose titration 10 mg for 1 week - 20 mg for 1 week - 30 mg for 6 weeks BID) compared to corresponding placebo in subjects with a diagnosis of UI.

2.2 Secondary Objective

The secondary objective of this study is to explore efficacy of litoxetine (dose titration 10 mg for 1 week - 20 mg for 1 week - 30 mg for 6 weeks BID) compared to corresponding placebo in subjects with a diagnosis of UI.

2.3 Primary Endpoint(s)

Safety:

1. Incidence and severity of AEs and Adverse Events of interest (urinary retention, withdrawal symptoms) over the course of the study. AEs are recorded at visits 2,3,4,5,6 and 7.
2. Adverse Events of special psychiatry interest (nervousness, anxiety, panic attacks, insomnia, aggression, mania, suicidal ideation, development/worsening of depression) over the course of the study
3. Suicidal Adverse Events and Adverse Events suggestive of abuse potential will be analysed, and detailed narratives provided
4. Lab parameters: Haematology and chemistry recorded at visit 1,2,6 and 7. Urinalysis recorded at visit 1 and 2.
5. Absolute change from end of the Screening Placebo Run-In Period in ECG readings and Week 8 (Visit 6). ECG parameters of interest include: ventricular rate, QT interval, corrected QT interval, PR interval, and QRS duration
6. Absolute change from end of the Screening Placebo Run-In Period to each visit in standardised cuff systolic and diastolic blood pressure and radial heart rate

2.4 Secondary Endpoints(s)

Efficacy:

1. Percentage change from end of the Screening Placebo Run-In Period to Week 8 (Visit 6) in the number of incontinence episodes in a week
2. Absolute change from end of the Screening Placebo Run-In Period to Week 8 (Visit 6) in the number of incontinence episodes/24 hours (daily average)
3. Proportion of subjects who become continent at Week 8 (Visit 6)
4. Change from end of the Screening Placebo Run-In Period to Week 8 (Visit 6) in the total number of incontinence pads used per week
5. Percentage change from end of the Screening Placebo Run-In Period to Week 8 (Visit 6) in the number of nocturia episodes in a week.

3. Study Design

This is a Phase 1/2a, double-blind, randomised, placebo-controlled, parallel-group study in subjects 18 to 70 years old diagnosed with UI.

The study will include a 2-week, single-blind (subject blind) Screening Placebo Run-In Period and an 8-week double-blind Treatment Period. The Treatment Period will be followed by a 1 week Dose-tapering Period and subjects will return to the clinic for a safety Follow up Visit 4 weeks after treatment is completed. This provides a total study duration of 15 weeks. No interim analysis is planned.

All subjects will enter the Screening Placebo Run-In Period during which eligibility will be assessed and single blind placebo run-in medication will be provided. In the latter half of this period, the subject will complete 7 days of bladder diary to capture incontinence events and pad usage. Subjects who continue to meet eligibility criteria after the Screening Placebo Run-In period, will enter the Treatment Period and be randomly assigned (2:1) to receive study drug (litoxetine10 mg, 20 mg, 30mg) or matching placebo BID.

Litoxetine or placebo treatment will be provided with dose titration, starting with 10 mg BID for 1 week, escalated to 20 mg BID for 1 week, and subsequently escalated to 30 mg BID for 6 weeks' duration (for a total treatment period of 8 weeks).

If the subject does not tolerate the last dose level escalation (i.e. cannot tolerate 30 mg BID), the dose can be reduced to the previous dose level (20 mg BID). If the patient does not tolerate the lower dose level (20 mg BID) s/he will be discontinued from the study. After 8 weeks of treatment, doses will be reduced by 50% over 1 week to taper off treatment. A safety follow up visit will occur 4 weeks after treatment is permanently stopped (total study duration 15 weeks).

Safety assessments will be conducted throughout the trial and will include physical examinations, vital signs, evaluation of psychiatric status (suicidality, depression symptoms, anxiety and sleep related symptoms), clinical laboratory evaluations, 12-lead electrocardiograms (ECGs), and adverse events (AEs).

Efficacy will be assessed by number of urinary incontinence episodes and the number of incontinence pads used, recorded at Baseline (V2) and endpoint (V6).

A schedule of assessments is provided in Figure 1.

A schematic of the study design is presented in Figure 2.

Figure 1: Schedule of Assessment

Visit Number	Visit 1 ⁽¹⁾	Visit 2 ⁽¹⁾	Visit 3	Visit 4	Visit 5	Telephone contact	Visit 6	Visit 7
Visit Name	Screening/ Placebo Run In	Eligibility assessment/ Randomization (start 10 mg litoxetine or Placebo BID)	1 week Post Randomization First dose escalation (start 20 mg or Placebo BID)	2 weeks Post Randomization Second dose escalation (start 30 mg or Placebo BID)	3 weeks Post Randomization		8 weeks post Randomization Final Treatment Visit⁽⁴⁾ (ET Visit)	13 weeks post Randomization Post-Treatment Safety F/U⁽³⁾ (End of Study Visit)
Study Day ⁽²⁾	Day 0	Day 14	Day 21	Day 28	Day 35	Day 42	Day 70	Day 105
Signed informed consent	X							
Demographics (incl body weight and height, BMI)	X						X ⁽¹³⁾	X ⁽¹³⁾
Complete C-SSRS, BDI-II, BAI, PSQI ¹⁶	X	X	X	X	X	X (C-SSRS only)	X	X
Medical / surgical/ smoking history	X							
Urinary and incontinence history	X							
Prior and concomitant medication recording	X	X	X	X			X	X

Figure 1: Schedule of Assessment

Visit Number	Visit 1 ⁽¹⁾	Visit 2 ⁽¹⁾	Visit 3	Visit 4	Visit 5	Telephone contact	Visit 6	Visit 7
Visit Name	Screening/ Placebo Run In	Eligibility assessment/ Randomization (start 10 mg lítoxetine or Placebo BID)	1 week Post Randomization First dose escalation (start 20 mg or Placebo BID)	2 weeks Post Randomization Second dose escalation (start 30 mg or Placebo BID)	3 weeks Post Randomization		8 weeks post Randomization Final Treatment Visit⁽⁴⁾ (ET Visit)	13 weeks post Randomization Post-Treatment Safety F/U⁽³⁾ (End of Study Visit)
Study Day ⁽²⁾	Day 0	Day 14	Day 21	Day 28	Day 35	Day 42	Day 70	Day 105
Vital signs ⁽¹¹⁾	X	X	X	X	X		X	X
Physical examination	X	X	X	X	X		X	X
PVR	X	X					X	
Pregnancy test ^(5,6)	X	X	X	X			X	X
Urinalysis (dipstick) ⁽¹⁰⁾	X	X						
Haematology and biochemistry ⁽⁸⁾	X	X	X ⁽¹⁵⁾	X ⁽¹⁵⁾	X ⁽¹⁵⁾		X	X ⁽⁹⁾
ECG (resting, 12-lead)	X	X	X	X	X		X	X ⁽⁷⁾
Evaluation of eligibility/randomization	X	X						
Dispensing/collection of trial drug	X	X	X	X			X ⁽¹⁴⁾	X

Figure 1: Schedule of Assessment

Visit Number	Visit 1 ⁽¹⁾	Visit 2 ⁽¹⁾	Visit 3	Visit 4	Visit 5	Telephone contact	Visit 6	Visit 7
Visit Name	Screening/ Placebo Run In	Eligibility assessment/ Randomization (start 10 mg litoxetine or Placebo BID)	1 week Post Randomization First dose escalation (start 20 mg or Placebo BID)	2 weeks Post Randomization Second dose escalation (start 30 mg or Placebo BID)	3 weeks Post Randomization		8 weeks post Randomization Final Treatment Visit⁽⁴⁾ (ET Visit)	13 weeks post Randomization Post-Treatment Safety F/U⁽³⁾ (End of Study Visit)
Study Day ⁽²⁾	Day 0	Day 14	Day 21	Day 28	Day 35	Day 42	Day 70	Day 105
Patient bladder diary review/collection ⁽¹²⁾	X	X					X	
Recording of AEs		X	X	X	X		X	X

Abbreviations: AEs = adverse events; BMI = body mass index; ECG = electrocardiogram; ET = early termination; PVR = postvoid residual urine volume; UTI = urinary tract infection

(1) Eligible subjects will undergo a 2-week Screening Placebo Run-In Period with 7 days bladder daily diary symptom collection. Subjects who continue to be eligible after the Screening Placebo Run-In Period will be randomised (Treatment Period).

(2) Visit window \pm 2 days

(3) AEs must be followed for a minimum of 30 days and until complete resolution or stabilization of the event, or as deemed appropriate by the Investigator on consultation with the Sponsor medical responsible.

(4) If a subject is withdrawn prematurely from the trial, all procedures indicated for the Week 8 (Visit 6) visit must be performed. The Investigator should use every effort to encourage the subject to taper study medication for 1 week and to return for the Safety Follow-up Visit (Visit 7).

(5) Serum pregnancy tests will be performed prior to entry into the trial (Visit 1), the ET Visit (Visit 6; if the subject is discontinuing the study) and at the End of Study Visit (Visit 7) for all female subjects of childbearing potential. Only those female subjects with a negative pregnancy test at Visit 1 will receive trial medication.

(6) Urine (dipstick) pregnancy tests will be performed at Visits 2, 3, 4, 5, and 6 (if it is not the ET Visit) for all female subjects of childbearing potential. Only those female subjects with a negative pregnancy test will receive trial medication.

(7) ECG at Follow-up (Visit 7) is only required if ECG was abnormal at Week 8 (Visit 6) and the abnormality represents a clinically significant worsening from baseline.

(8) Blood samples will be taken in a fasting state at Screening, Day 14 (Visit 2) and Week 8 (Visit 6).

(9) Laboratory tests at Follow-up (Visit 7) are only required if labs were abnormal at Week 8 (Visit 6) and the abnormality represents a clinically significant worsening from baseline.

(10) If Urine Dipstick is positive for nitrates and leukocyte esterase, take history of signs and symptoms of UTI, and perform urine culture. If urine culture and clinical signs and symptoms are positive, the subject cannot be included, but can be re-screened at a later date as long as the subject does not meet exclusion criterion 3 (4 or more UTIs in the past 12 months).

(11) Vital signs include blood pressure, heart rate, and body temperature.

(12) At Visit 1, the patient is informed how to use the bladder diary. During the 7 days prior to Visit 2 and Visit 6 the following urinary incontinence information will be recorded in the bladder diary: the number of incontinence episodes/pads used daily.

[figure not shown]
(13) Weight only.

(14) Dispense study drug for the 1-week tapering period (half of the dose to which the subject is randomized).

(15) Electrolytes (including sodium) only.

(16) In addition to the visit assessments detailed above, suicide monitoring using the C-SSRS will also be performed by a telephone contact with the subject 4 weeks post randomization (study day 42).

Figure 2: Study Design

BID = twice daily

3.1 Sample Size

Approximately 95 subjects are expected to be enrolled into the 2-week, single-blind (subject blind) Screening Placebo Run-In Period. It is expected that 20% of subjects will not qualify for randomization after Screening Placebo Run-In.

The study is expected to randomize approximately 78 subjects into the double-blind treatment where subjects will be allocated to litoxetine (dose titration over 10 mg, 20 mg, 30mg) or matched placebo BID in a 2:1 ratio. A post randomisation dropout rate of 30% has been estimated, resulting in 60 evaluable subjects.

A sample size of 60 subjects is expected to provide a 95% confidence interval for a rate of safety events of 50% with a width +/- 14%. The sample size calculation is based on the precision of the estimate of the primary outcome, safety events, using a rate of 50% which would provide the most conservative sample size.

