8.10 Determination of Sample Size

Approximately 95 subjects are expected to be enrolled into the 2-week, single-blind (subject blind) Screening Placebo Run-In Period. It is expected that 20% of subjects will not qualify for randomization after Screening Placebo Run-In.

The study is expected to randomize approximately 78 subjects into the double-blind treatment where subjects will be allocated to litoxetine (dose titration over 10 mg, 20 mg, 30mg) or matched placebo BID in a 2:1 ratio. A post randomisation dropout rate of 30% has been estimated, resulting in 60 evaluable subjects.

This sample size will provide confidence intervals for the rate of safety events that are +/- 14% for the widest observed intervals in the treatment arm.

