4.1 Study Populations

The study population will consist of subjects with UI. Subjects must be able to provide written consent and meet all the inclusion criteria and none of the exclusion criteria.

A valid efficacy measurement is defined as a valid number of incontinence episodes as recorded in the bladder diary and uploaded in the eCRF at Visit 2 and Visit 6, i.e. either as 0 or greater than 0.

There are 4 analysis populations for this study:

Randomised population:

Defined as all subjects randomised to treatment (Visit 2).

Safety population:

Defined as all subjects who are randomised to treatment (Visit 2), receive study drug, and undergo at least 1 visit.

Intent-to-Treat (ITT) population:

Defined as all subjects who are randomized to treatment (Visit 2), receive at least one dose of study drug and have a valid efficacy measurement at Baseline (Visit 2).

Per Protocol (PP) population:

Defined as those subjects who are randomised, receive at least one dose of study drug, provide a valid efficacy measurement at Baseline (Visit 2) and a valid end of study primary efficacy endpoint (Visit 6), and have completed the study without a major protocol deviation.

The following populations are defined for analysis purposes:

1. Enrolled Population: each subject that signed the Informed Consent form and entered the Screening Period.
2. Completers Population: each subject that completed the trial, per protocol.
3. Full Analysis Set Population: each subject which is in either ITT or PP population.

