6.7 Safety Analysis

The general objectives of this study are to establish the safety, tolerability and efficacy of litoxetine in men and women who suffer from UI. The primary analyses will focus on safety, describing the adverse events with point estimates and Clopper Pearson 95% confidence intervals. All safety analyses will be conducted on the safety population.

All AEs will be coded using the MedDRA dictionary (version 20.1).

1. Incidence and severity of Treatment Emergent Adverse Events and Treatment Emergent Adverse Events of interest (urinary retention, withdrawal symptoms) over the course of the study.

The Treatment Emergent Adverse Events (TEAEs) and the TEAEs of Interest will be summarised by treatment group. The SOCs and PTs will be used for tabulation. The number of TEAEs/TEAEs of interest and the number and the percentage of patients with at least one AE will be presented by SOC and PT for each treatment group. Within each SOC and PT, the highest severity grade attained will be reported, for AEs with divergent severities.

TEAEs/TEAEs of interest will be described with point estimates and Clopper Pearson 95% confidence intervals.

The analysis of treatment emergent adverse events is the primary safety endpoint, the analysis of TEAEs of interest is considered as part of the secondary safety analysis.

2. Treatment Emergent Adverse Events of special psychiatry interest (nervousness, anxiety, panic attacks, insomnia, aggression, mania, suicidal ideation, development/worsening of depression) over the course of the study

The Treatment Emergent Adverse Events of special psychiatry interest will be summarised by treatment group. The SOCs and PTs will be used for tabulation. The number of AEs and the number and the percentage of patients with at least one AE will be presented by SOC and PT for each treatment group. Within each SOC and PT, the highest severity grade attained will be reported, for AEs with divergent severities.

Adverse events will be described with point estimates and Clopper Pearson 95% confidence intervals.

3. Treatment Emergent Suicidal Adverse Events and Adverse Events suggestive of abuse potential

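### Thirty per cent dropout from 78 randomised leaves about 55 evaluable subjects, not 60, and the ±14% safety precision is tied to different denominators in different sections

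*SAP*

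**What the plan says.** SAP 3.1 sets out the flow of subjects in steps. It begins: "Approximately 95 subjects are expected to be enrolled into the 2-week, single-blind (subject blind) Screening Placebo Run-In Period". A run-in failure rate of 20% is assumed. About 78 are then randomised 2:1 to litoxetine or placebo. The last step is: "A post randomisation dropout rate of 30% has been estimated, resulting in 60 evaluable subjects". The same chain of numbers is in SAP 1.6, in the protocol synopsis under Number of Subjects, and in protocol 8.10.

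The size is justified by the precision of the safety event rate, and the three sections that give this figure do not describe it alike:

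- SAP 3.1 says that a sample of "60 subjects is expected to provide a 95% confidence interval for a rate of safety events of 50% with a width +/- 14" per cent.
- SAP 1.6 says that the sample size should give "confidence intervals for the most conservative rate of safety events (50%) that are +/- 14% for the widest observed intervals in the treatment arm".
- Protocol 8.10 says that it will give "confidence intervals for the rate of safety events that are +/- 14% for the widest observed intervals in the treatment arm".

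Two other parts of the SAP decide who counts in that interval. SAP 4.1 gives the safety population as: "Defined as all subjects who are randomised to treatment (Visit 2), receive study drug, and undergo at least 1 visit". SAP 6.7 adds: "All safety analyses will be conducted on the safety population". SAP 6.3 and 6.7 specify Clopper-Pearson 95% intervals and summaries by treatment group.

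**The concern.** There are two separate faults.

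First, 78 randomised, 30% dropout and 60 evaluable cannot all be right.

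Second, the same ±14% is given two denominators. In SAP 3.1 it rests on 60 subjects, which is the two-arm evaluable total from the sentence before. In SAP 1.6 and protocol 8.10 it rests on the treatment arm. In those two sections the reference to the sample size comes directly after the 60 evaluable subjects, so a reader could take the arm to be 40 subjects (two thirds of 60), 52 (two thirds of 78), or something else.

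Safety is the primary endpoint, and this precision statement is the only rationale given for the size of the trial; there is no power calculation. The figure, its denominator and the counts that feed it should agree between the two documents and within the SAP.

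**Working it through.** **Inputs.** About 95 entering run-in, 20% run-in failure, about 78 randomised, 30% dropout, 60 evaluable (SAP 3.1). Allocation 2:1 (SAP 3.2). Event rate 50% and half-width 14% (SAP 1.6 and 3.1). Clopper-Pearson 95% intervals (SAP 6.3 and 6.7; protocol 8.1).

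**Step 1: run-in.** 95 × (1 − 0.20) = 76, against 78 stated. The plan gives both counts as approximate, and this gap is within that.

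**Step 2: dropout.** Evaluable = randomised × (1 − dropout) = 78 × 0.70 = 54.6, about 55. The plan states 60, which is 5.4 more (5.4 / 54.6 = 10%). In reverse, the dropout that leaves 60 of 78 is 1 − 60/78 = 23.1%. The stated pair does reproduce as 60 × 1.30 = 78. This suggests, though neither document says so, that 60 was multiplied by 1.30 instead of divided by 0.70.

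**Step 3: candidate denominators.**

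- Both arms, evaluable as stated: 60
- Litoxetine share of 60: 60 × 2/3 = 40
- Litoxetine share of 78: 78 × 2/3 = 52

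**Step 4: precision at a 50% rate.** For x events in n subjects, the Clopper-Pearson limits are the 2.5% quantile of Beta(x, n − x + 1) and the 97.5% quantile of Beta(x + 1, n − x). The half-width is half the distance between them. The Wald half-width, 1.96 × √(0.25/n), is shown for comparison.

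| Basis | x/n | Clopper-Pearson 95% limits | Half-width | Wald half-width |
|---|---|---|---|---|
| Both arms, 60 | 30/60 | 0.368 to 0.632 | 13.2% | 12.7% |
| Litoxetine among 60 | 20/40 | 0.338 to 0.662 | 16.2% | 15.5% |
| Litoxetine among 78 | 26/52 | 0.358 to 0.642 | 14.2% | 13.6% |

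The stated ±14% is reproduced by 52 under either method. It is not reproduced by 60 or by 40 under either.

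**Step 5: which denominator the analysis will use.** The safety population requires randomisation, study drug and at least one visit. It does not require completion. A treated subject who leaves later still counts, so the planning denominator for the litoxetine interval is close to 52.

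**The case against.** The dropout arithmetic has no good defence. Words such as approximately and estimated do not cover a gap of five subjects. The stronger objections concern the precision figure and the remedy.

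- **The SAP 3.1 sentence errs on the safe side.** Sixty subjects give 13.2%, so ±14% overstates the uncertainty by less than one point, and the sentence does not use the word pooled. This is true, but 60 is plainly the two-arm total, and SAP 1.6 in the same document names the treatment arm.
- **Fifty-two is inferred.** Neither document states it, and other sizes also round to 14%. Among even n, these run from 50 (14.5%) to 56 (13.7%). The corrected evaluable total of 55 would round to 14% as well (27/55 gives 13.8%). This stands as a caution about what the authors had in mind. But 55 is a two-arm count, while adverse events are summarised by treatment group and two of the three statements refer to the treatment arm. Fifty-two is the 2:1 share of the planned 78.
- **Fifty-two is a ceiling.** Three litoxetine subjects without a dose or a visit would leave 49, with a half-width of 14.6%. This is correct and small, and it is why the wording should say about.
- **A third reconciliation exists.** Keeping both 60 and 30% requires 60/0.70 = 85.7, or 86 randomised. That is arithmetically valid, but it changes enrolment, and the litoxetine safety precision does not need it.
- **The efficacy loss may be smaller than it looks.** Neither document defines evaluable. Subjects who withdraw early are to have the Visit 6 procedures, including diary collection, and SAP 6.1 imputes missing Visit 6 episode counts in the ITT analysis. This stands, and it limits the consequence.

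**Conclusion.** Both faults hold. With 78 randomised and 30% dropout, about 55 subjects are evaluable. The stated 60 is about 5 too many (10%) and agrees only with 23.1% dropout. The ±14% is assigned to 60 subjects in one section and to the treatment arm in two others. It matches neither 60 (13.2%) nor the 40 litoxetine subjects within 60 (16.2%), but it does match the 52 randomised to litoxetine (14.2%).

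The consequence is modest. If nearly all randomised litoxetine subjects are dosed and attend a visit, safety precision in that arm stays at about ±14%. The dropout error mainly overstates how many subjects can be expected to have Week 8 diary data, which serves a secondary, exploratory aim. The statements should still be corrected, because they are the trial's only sizing rationale and concern its primary endpoint.

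**What to change.** **Dropout sentence** (protocol synopsis, protocol 8.10, SAP 1.6, SAP 3.1): keep 30% and give about 55 evaluable subjects. If 60 is the intended figure, give the dropout as 23% instead.

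**Precision sentence:** in SAP 3.1, replace the 60 subjects with about 52 litoxetine subjects in the safety population, and state that the 95% half-width at a 50% rate is about 14% by Clopper-Pearson. In SAP 1.6 and protocol 8.10, replace the reference to the sample size with the same basis.

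**Cost:** wording only, in four places. Enrolment, analysis sets and methods do not change. Either the expected evaluable count falls from 60 to about 55 or the stated dropout falls to 23%, and the ±14% for litoxetine stays.
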